### III. Inclusion/exclusion criteria.

- a. Inclusion criteria: obtaining prenatal care at UIC; initial prenatal hemoglobin between 10.0 – 11.9 g/dl; 18 - 45 years of age; spontaneous/natural conception; singleton pregnancy; < 20 weeks gestation; and willing to: a) fast for at least 2 hours prior to research data collection visits (3 occasions), b) agree to randomization; c) ingest Lp299v + standard PNVI or standard PNVI + placebo daily through delivery; c) refrain from **ALL** other supplements including other PNVs unless medically indicated (e.g., folate); d) attend 3 research data collection visits at UIC; e) undergo 3 venipunctures; and f) come to UIC on 4-5 occasions (separate from research visit but will be coordinated around standard clinical care visits) to pick up supplements and have study compliance monitored/checked. Women will also be able to read and write English, and have access to a smart phone. Also, women must agree to refrain from **ALL** other pre and probiotic supplements (unless medically indicated) including Activia yogurt, Kefir, Tropicana Probiotic, and Good Belly products while in the study.
- b. Exclusion criteria: Autoimmune disorder; current or previous premature rupture of membranes or clinical chorioamnionitis; current bacterial or viral infection; oral antibiotic use in the last 3 months; receiving steroid or anti-inflammatory treatment; previous bariatric surgery; malabsorptive condition; current hyperemesis; hematologic disorder (i.e., sickle cell disease or hemochromatosis); current tobacco use or within the past 1 month; current alcohol consumption; current drug use; or type 1 or 2 diabetes given these factors may influence the biological markers.

**IV. Randomization.** Women will be randomized to the Lp229V + standard PNVI or standard PNVI + placebo following the baseline visit.

**V. Treatment groups.** Women will be assigned to one of two treatment groups as described below.

- a. **Lp299v + standard PNVI.** Starting at 15-20 weeks gestation, women assigned to this group will consume Lp299v + standard PNVI capsules each, once daily, through delivery. Women will be asked to consume both pills with dinner along with a cold or room temperature beverage. The Lp299v supplement will be provided by NatureMade, Pharmavite. This probiotic formulation has a bacterial density of  $10^{10}$  colony forming units (CFUs) per capsule. The PNVI is from NatureMade, Pharmavite and the nutrient content is comparable to a standard prenatal plus vitamin prescribed by clinicians at UIC. The PNVI contains 27 mg of iron as ferrous fumarate. The pills will be provided in separate Pillsy containers and labeled as Vitamin and just generically as “supplement”. Women will receive 30-40 days of pills at the baseline visit and asked to start taking the pills on the 1st day of the 15th-20th gestational week. [name], Associate Professor of Clinical Obstetrics & Gynecology at UIC and Director of the Center for Women’s Health, will write the prescription for both the Lp299v and standard PNVI. The UIC Pharmacy will fill the prescription and deliver to the CRC. Women will pick up new pills at UIC every 28 days during a scheduled standard care prenatal visit or during a separate pill pick up or research data collection visit. If necessary, research staff will hand deliver supplements to the participant home if requested.
- b. **Standard PNVI + placebo.** Starting at 15-20 weeks gestation, women assigned to this group will consume standard PNVI + placebo once daily, through delivery. Taste and packing of the placebo will be identical to the Lp299v, minus the Lp299v, and will be produced by the UIC Pharmacy. Women will be asked to consume both pills with dinner along with a cold or room temperature beverage. The PNVI is from NatureMade, Pharmavite. The PNVI nutrient content is comparable to a standard prenatal plus vitamin prescribed by UIC clinicians. The PNVI contains 27 mg of iron as ferrous fumarate. The pills will be provided in separate Pillsy containers and labeled as Prenatal Vitamin Tablets and Probiotic or Placebo Capsules. Women will receive 30 days of pills at the baseline and asked to start taking the pills on the 1st day of the 15th-20th gestational week. Women will pick up new pills at UIC every 28 days and whenever possible during a scheduled standard

care prenatal visit or during a separate pill pick up or research data collection visit. If necessary, research staff will hand deliver supplements to the participant home if requested.

Supplement Facts		
Serving Size 1 Tablet		
Amount Per Tablet		% Daily Value for Pregnant and Lactating Women
Vitamin A (as Beta Carotene)	2567 IU	32%
Vitamin C (as Ascorbic Acid)	85 mg	142%
Vitamin D 3 (as Cholecalciferol)	1000 IU	250%
Vitamin E (as dl-Alpha Tocopheryl Acetate)	33 IU	110%
Vitamin K (as Phytonadione)	90 mcg	*
Thiamin (as Thiamin Mononitrate)	1.4 mg	82%
Riboflavin	1.4 mg	70%
Niacin (as Niacinamide)	18 mg	90%
Vitamin B 6 (as Pyridoxine Hydrochloride)	1.9 mg	76%
Folic Acid	800 mcg	100%
Vitamin B 12 (as Cyanocobalamin)	5.2 mcg	65%
Biotin	30 mcg	10%
Pantothenic Acid (as d-Calcium Pantothenate)	6 mg	60%
Calcium (as Calcium Carbonate)	250 mg	19%
Iron (as Ferrous Fumarate)	27 mg	150%
Iodine (as Potassium Iodide)	150 mcg	100%
Magnesium (as Magnesium Oxide)	45 mg	10%
Zinc (as Zinc Oxide)	11 mg	73%
*Daily value not established		

No Color Added • No Artificial Flavors • No Yeast • Gluten Free  
Nature Made Multi Prenatal provides key vitamins and minerals for nutritional support before and during pregnancy.†  
**SUGGESTED USE:** Take one tablet daily with a meal. For easier swallowing, take with water before and during ingestion. Keep bottle tightly closed. Store in a cool, dry place. Do not use if imprinted seal under cap is broken or missing.

**WARNING:** Accidental overdose of iron-containing products is a leading cause of fatal poisoning in children under 6. Keep this product out of reach of children. In case of accidental overdose, call a doctor or poison control center immediately.

**OTHER INGREDIENTS:** Cellulose Gel, Corn Starch, Maltodextrin, Hydrogenated Soybean Oil, Dibasic Calcium Phosphate, Croscarmellose Sodium, Hypromellose, Silicon Dioxide, Gelatin, Magnesium Stearate, Polyethylene Glycol.

Distributed by:  

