**Specific Aim 1:** To determine the impact of consuming daily Lp299v + standard PNVI vs. standard PNVI + placebo beginning between 15-20 weeks gestation through delivery on maternal iron status and metabolism. To fully characterize maternal iron metabolism and regulators of maternal iron metabolism we will measure several blood-based markers including hemoglobin, hematocrit, ferritin, transferrin receptor, transferrin saturation, serum iron, erythropoietin, systemic inflammation and hepcidin at baseline, 24-28 and 34 - 36 weeks gestation, and at

delivery. *Hypothesis: Women consuming Lp229v will have superior iron status at –24-28 and 34 - 36 weeks gestation and at delivery compared to control women.*

**Specific Aim 2:** To determine colonization and propagation of the gut microbial community with Lp299v from rectal swabs collected at baseline, 24-28 weeks and 34 - 36 weeks gestation in women consuming Lp299v + standard PNVI vs. standard PNVI + placebo. *Hypothesis: Women consuming LP299v will have greater colonization and propagation of Lp299v in their rectal swabs at –24-28 week and 34 - 36 weeks gestation compared to women consuming PNVI + placebo.*

**Specific Aim 3:** To explore the effect of daily oral Lp299v vs. placebo on infant iron status at delivery. Infant iron status will be measured (via cord blood at delivery) (i.e., hemoglobin, ferritin, transferrin, serum iron, and transferrin receptor). *Hypothesis: Infant of women consuming LP299v will have higher iron status at delivery.*

**Specific Aim 4:** To determine the feasibility and tolerability of daily oral Lp299v supplementation (15-20 weeks gestation-delivery). *Hypothesis: Feasibility and tolerability will be high in both treatment groups of the study for the duration of the trial.*

**Exploratory Aim 1:** There is some evidence that probiotic use can positively influence maternal health outcomes including mood. We will explore differences in the development of gestational hypertension, pre-eclampsia, and gestational diabetes using data extracted from the electronic health record (EHR). We will also examine changes to maternal stress response (i.e., serum 17-hydroxycorticosterone and hair cortisol via immunoassay) and self-reported stress, depression, anxiety, resilience, experiences of discrimination, childhood trauma, social support, post-traumatic stress, and spirituality via surveys in women consuming Lp299v + standard PNVI vs. standard PNVI + placebo.

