## 2. Methods.

- I. **Research participants.** We will recruit and enroll 40 women early in pregnancy (< 20 weeks gestation) from the University of Illinois at Chicago (UIC) Obstetrics (OB) clinics located at the University of Illinois Hospital and Health Sciences System (UIHHSS) Outpatient Care Center, Center for Women’s Health. Women will be between the ages of 18 – 45 years old and at risk for maternal ID based on hemoglobin of 10.0 – 11.9 g/dl assessed as part of standard clinical care during the first prenatal OB visit.
- II. **Eligibility, recruitment, and informed consent:** After obtaining a waiver of consent for recruitment purposes, we will complete a pre-screen eligibility checklist of women < 20 weeks gestation who are seeking prenatal care at the UIC Obstetrics Clinics at the UIHHSS Center for Women’s Health. Potentially eligible women will be identified through clinic schedules and eligibility assessed via Cerner/EHR (only if data is available, data will not be available for new UIC patients). Women identified as potentially eligible through the EHR data or new UIC patients attending their first OB prenatal appointment will be approached in clinic. A research team member will introduce the study, assess interest, and further determine eligibility using a screening checklist. Interested and eligible women will be asked to provide contact information. As part of routine care, maternal hemoglobin will be assessed following the first OB visit. For women that express interest in the study and provide contact information, hemoglobin results will be followed up in Cerner. Women will be called regardless of their results to report on continued study eligibility. If hemoglobin is within the study defined range (10.0 – 11.9 g/dl) women will be invited to participate. Those who continue to express interest will be asked to schedule a baseline appointment at the UIC Clinical Research Center (CRC)s. Women will be consented at the baseline visit. Research personnel will explain to every eligible woman that their choice to participate will in no way affect their standard of care at UIHHS.

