***b. Research follow-up visits (24–28 and 34–36 weeks gestation)***

Reminder Phone Call, Text, and Email: Women will be called or texted and emailed 2-3 days before the visit. Women will be reminded of their appointment time and location, asked to not eat for at least 2 hours before the appointment, and reminded about the visit procedures.

Data collection procedures: Women will be weighed with an electronic scale; a venous blood sample (30 ml) obtained by research staff; 2 rectal swab samples collected, optional; and surveys (described in detail below) will be interviewer administered by trained staff. If there is extra blood available from the venous blood sample and the patient consents, it may be used for future research to learn more about how to prevent, detect, or treat other health problems in pregnancy.

Surveys: Women will be asked to complete the following surveys:

1. 24 hour diet recall. The 24-hour diet recall will be collected using Nutrition Data System for Research (NDSR) software, a computer-based software application developed at the University of Minnesota that facilitates the collection of dietary recalls in a standardized fashion. Dietary intake data gathered by interview is governed by a multiple-pass interview approach. Dietary supplement use will be assessed in conjunction with collection of 24-hour dietary recalls using

the Dietary Supplement Assessment Module included in NDSR. Use of all types of dietary supplements and non-prescription antacids are queried in the module. The RAs are NDSR certified through the University of Illinois Cancer Center Diet and Behavior Shared Resource.

2. GI symptoms checklist. This short survey probes for recent GI problems including abdominal pain, nausea, constipation, and diarrhea.
3. Mood and Anxiety Symptom Questionnaire – Anhedonia subscale (MASQ-AD). This is a 22-item subscale of the MASQ, is a measure of depressive disorders.
4. Patient Health Questionnaire (PHQ-9). This is a 9-item questionnaire assessing depressive symptoms.
5. Edinburgh Postnatal Depression Scale (EPDS). This is a 10-item scale intended to measure depressive symptoms during the perinatal period.
6. Perceived stress scale. This is a 10-item scale intended to measure perceived stress over the last month.

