**e. Labor and delivery.**

Reminders for contacting research staff and participant tracking. During the 34–36 gestational week research visit and/or at the final pill pick, women will be provided a laminated card with the study number and staff personal contact information. Women will be instructed to contact the research team when they are admitted to UIC labor and delivery. In addition, we will follow the progress of these women closely via phone call, text message, email and through the patient EHR until they are admitted to UIC labor and delivery. UIC labor and delivery staff will also be in-serviced regarding the study procedures.

- 1) Maternal venous blood draw: Following admission, as part of routine care, women will undergo a venous blood collection by labor and delivery staff. As part of this routine care, we will request an additional two tubes of blood (30 ml) for research purposes. If there is extra blood available from the venous blood sample and the patient consents, it may be used for future research to learn more about how to prevent, detect, or treat other health problems in pregnancy.
- 2) Umbilical venous cord blood collection (placental cord blood): Immediately following delivery, the research team will collect a maximum of three tubes of umbilical venous cord blood (~30 mL). If a research participant chooses to bank their umbilical cord blood, and therefore the research team cannot obtain 30 mL of umbilical cord blood, the research team will draw 30 mL of placental blood for analysis. If there is extra cord blood available from the cord blood sample and the patient consents, it may be used for future research to learn more about how to prevent, detect, or treat other health problems in pregnancy.
- 3) Placenta (20 grams): After the cord blood has been obtained, the placenta will be placed in a basin with lid and transferred to the [name] lab space in COMRB. Following placental

characteristics will be examined (i.e., weight, length) and processed for analysis and stored at -80C until later analysis.

- 4) Maternal and infant labor and delivery data: Following participant discharge, a research team member will abstract pertinent maternal and infant L&D data (i.e., route of delivery, infant weight, and infant length) from the EHR.

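### Eligibility does not ask where a woman plans to deliver, although the Aim 3 outcome and the Aim 1 delivery value can, as written, be collected only at UIC labor and delivery

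*Combined protocol and SAP*

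**What the plan says.** **Eligibility (2. Methods, III.a).** The only site criterion is the opening one: "Inclusion criteria: obtaining prenatal care at UIC; initial prenatal hemoglobin between 10.0 – 11.9 g/dl". The list of undertakings that follows covers fasting, randomization, daily supplements, avoiding other supplements, pick-up trips, and the visits and blood draws: "attend 3 research data collection visits at UIC; e) undergo 3 venipunctures". Delivery is mentioned only as the end of supplement use. Planned place of delivery does not appear.

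**What the aims need (section 1).** The Aim 1 hypothesis is that women on Lp299v "will have superior iron status at –24-28 and 34 - 36 weeks gestation and at delivery compared to control women". For Aim 3, "Infant iron status will be measured (via cord blood at delivery", and no other source is given.

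**How delivery samples are obtained (2. Methods, VI.e).** "Women will be instructed to contact the research team when they are admitted to UIC labor and delivery". UIC labor and delivery staff are briefed on the procedures, maternal blood is added to the routine admission draw ("we will request an additional two tubes of blood (30 ml) for research purposes"), and the research team collects the cord blood. The COVID-19 changes, item 5, rely on specified midwives who are on duty when the woman is admitted for delivery. The one stated fallback is placental blood when a woman banks her cord blood. Neither section gives a route for samples from another hospital.

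**Size and analysis.** "We will recruit and enroll 40 women early in pregnancy". Section XIII compares infant iron status between groups by Student's t-test and the maternal markers by repeated-measures ANOVA and ANCOVA. It has no rule for samples that were never collected; the imputation it mentions is for undetectable levels.

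**The concern.** The eligibility list is detailed, down to particular yogurt products, yet it omits the one circumstance on which a whole aim depends. Randomization follows the baseline visit, before 20 weeks. A woman who already intends to deliver at another hospital meets every criterion, takes one of 40 places, and is then certain to be missing the delivery data if she keeps to her plan.

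Aim 3 has one measurement per infant, so such a woman contributes nothing to it. For Aim 1 she lacks the last time-point. If the repeated-measures ANOVA were run on complete cases, which the plan neither states nor rules out, her earlier values would be lost too. The loss is foreseeable and could be avoided by one question before randomization.

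**Working it through.** **Step 1. Criteria against needs.**

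| Needed for | Sample | Place of collection in the protocol | Covered by III.a? |
|---|---|---|---|
| Aim 1, baseline, 24-28 and 34-36 weeks | Maternal blood | UIC research visits | Yes: three visits, three venipunctures |
| Aim 1, delivery | Extra tubes from the routine admission draw | UIC labor and delivery | Planned site not asked |
| Aim 3 | Cord blood | UIC labor and delivery | Planned site not asked |

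The count of three venipunctures is correct: it matches the three research visits, and the delivery tubes come from a draw made for routine care. The gap is the place of delivery.

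**Step 2. Inputs for the size of the loss.** The plan states no power, effect size, SD or dropout allowance, so there is no planned figure to reproduce. From the documents: 40 women; two-sided 0.05; t-test for Aim 3. From VI.c: a feasibility limit of 15% withdrawal, used here as a scenario because it is not a sample-size input. Assumed: 1:1 allocation, 80% power, and 5-15% of retained women delivering elsewhere.

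**Step 3. Numbers left.**
- All 40 women: 20 + 20.
- At the withdrawal limit: 40 × 0.85 = 34, or 17 + 17.
- 5% of 34 elsewhere: 34 × 0.95 = 32.3, about 32, or 16 + 16.
- 15% of 34 elsewhere: 34 × 0.85 = 28.9, about 29, or 15 + 14.

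**Step 4. Detectable difference.** The normal approximation is d = (1.960 + 0.842) × √(1/n₁ + 1/n₂), in SD units. For 17 + 17, √(2/17) = 0.343 and d = 2.802 × 0.343 = 0.96. For 15 + 14, √(1/15 + 1/14) = 0.372 and d = 1.04. At these sample sizes the exact calculation with the noncentral t distribution is preferable.

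| Women with a cord sample | Normal approximation | Exact t |
|---|---|---|
| 20 + 20 | 0.89 SD | 0.91 SD |
| 17 + 17 | 0.96 SD | 0.99 SD |
| 16 + 16 (5% elsewhere) | 0.99 SD | 1.02 SD |
| 15 + 14 (15% elsewhere) | 1.04 SD | 1.08 SD |

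Relative to 17 + 17, the detectable difference grows by 1.02/0.99, about 3%, to 1.08/0.99, about 9%.

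**Step 5. A wider range.** If nobody withdrew and 10%, 20% or 30% of the 40 delivery samples were lost, 18, 16 or 14 per arm would remain, with exact-t detectable differences of 0.96, 1.02 and 1.10 SD.

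**The case against.** The strongest case against the point has four parts.

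- **The loss may be rare.** Women are recruited from UIC's own obstetric clinics and followed closely until admission. No rate of delivery elsewhere is given, so the scenario is an assumption. This stands.
- **The effect is small, in an exploratory aim.** Aim 3 is worded as exploratory, the protocol speaks of pilot testing, and there is no power target to miss. Starting from 34 women also treats a feasibility limit as if it were expected. That limit sits beside loss to follow-up, so women who move away may be counted twice. This stands too, and it keeps the point minor.
- **A baseline criterion cannot stop later changes.** Transfers for complications and moves happen after randomization. This stands: the criterion removes only losses already foreseeable at screening.
- **Reporting is partly in place.** Section XIII has visits completed and attrition compared between groups, and section XIV tracks reasons for dropout. Only a specific category for delivery elsewhere is missing.

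Three stronger readings are tempting, and the documents do not support them. A reader might take the three venipunctures as a miscount; as shown above, they are not. A reader might infer that women can refuse the delivery samples and still be randomized. The protocol does not label those samples optional, and the consent pages are not available, so this cannot be shown. A reader might also extend the point to Aim 2, because the swabs are voluntary ("2 rectal swab samples collected, optional"). That is a separate design choice, and the idea that refusal would follow symptoms under treatment is speculation.

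**Conclusion.** The point holds as a minor one. The criteria admit a woman who already plans to deliver at another hospital, and nothing in the protocol would then supply her Aim 3 outcome or her Aim 1 delivery value. That follows from the text alone.

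Its size does not follow from the text. With 34 women retained, 1:1 allocation and an assumed 5-15% delivering elsewhere, the Aim 3 detectable difference goes from 0.99 SD to about 1.02-1.08 SD. The case for acting rests on a modest loss of precision that can be avoided cheaply.

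A reader might infer that the comparison is biased. The documents do not show this. Women who plan another hospital before randomization hold that plan independently of their arm, so leaving them out costs mainly precision. Later transfers or moves could be related to outcome, but the documents give no evidence of how often they occur or whether they differ by arm, and the eligibility change would not prevent them.

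**What to change.** 1. **For women still to be enrolled:** add to III.a that the woman plans to deliver at UIC, and ask this at screening.
2. **For all women, including those already enrolled:** record the actual delivery site when the delivery data are abstracted. In the report, show by arm how many delivered elsewhere, as a separate reason for missing delivery samples alongside the attrition figures already planned.

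The cost is one screening line and one data field, with no new procedure. The downside is that a few women who plan another hospital become ineligible, and plans stated before 20 weeks may change. The documents do not say how many women remain to be enrolled, so the first change may have limited reach; the second applies regardless.

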**Nature Made Nutritional Products**  
[name], U.S.A.  
[name] • [www.NatureMade.com](http://www.NatureMade.com)

USP has tested and verified ingredients, potency and manufacturing process. USP sets official standards for dietary supplements. [www.uspverified.org](http://www.uspverified.org)

†This statement has not been evaluated by the Food and Drug Administration. This product is not intended to diagnose, treat, cure or prevent any disease.

**VI. Research-related visits.** Data will be collected at baseline (<20 weeks gestation), 24-28 and 34-36 weeks gestation and at delivery. Tolerability [potential adverse events (AEs) (e.g., GI symptoms)] will be assessed via phone/email/text weekly for the first 4 weeks and bi-weekly thereafter. Compliance data will be collected at pill pick-up visits (scheduled around usual care prenatal visits whenever possible) and during research visits. Women will be called or texted and emailed 2-3 days prior to each research-related visit and reminded of their appointment time, location and instructions how to prepare (e.g., fast for 2 hours, bring their pill containers). The visits will take place at the Clinical Research Center [name]. The research-related visits and data collected at each visit are described below:

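### The two arm descriptions give different container label wording, so staff who handle the bottles could infer the arm if the text is followed as written

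*Combined protocol and SAP*

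**What the plan says.** Section 2 (Methods), part V describes the two arms separately, and each description carries its own label sentence. For the Lp299v arm (V.a): "The pills will be provided in separate Pillsy containers and labeled as Vitamin and just generically as" supplement. For the placebo arm (V.b), the containers are "labeled as Prenatal Vitamin Tablets and Probiotic or Placebo Capsules". V.b also states: "Taste and packing of the placebo will be identical to the Lp299v, minus the Lp299v".

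The baseline supply is worded differently too. V.a has "Women will receive 30-40 days of pills at the baseline visit", while V.b has "Women will receive 30 days of pills at the baseline".

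Part VI asks women to bring their pill containers to research visits. It has staff count pills by hand at the pick-up visits and at the two follow-up research visits, and give the GI symptoms checklist at both kinds of visit. It has surveys administered by interviewers at the research visits. Tolerability, by contrast, "will be assessed via phone/email/text weekly for the first 4 weeks and bi-weekly thereafter".

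The COVID-19 changes dated 17 March 2020 move refills to courier and surveys to phone or an online link. They mention a labeled study bottle and generic capped bottles, but give no label text.

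**The concern.** A matched placebo is useful only if nothing else about the package reveals the arm. Here both containers, the vitamin and the study capsule, carry different words in the two arm descriptions. A pharmacy that took each description literally would print two sets of labels. A staff member who had seen both sets, or who knew the protocol, could then tell the arms apart while counting pills.

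What is at stake is the part of the data that depends on asking and recording: GI symptoms and adverse events reported at visits, and the stress, depression, anxiety and social support surveys given by interview. Knowledge of the arm can affect how such questions are put and how the answers are written down.

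**Working it through.** The plan gives no figure on this point, so the check sets the sections side by side.

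1. **Do the labels differ?** Yes, both of them. The vitamin container is called Vitamin in V.a and Prenatal Vitamin Tablets in V.b. The capsule container is called supplement in V.a and Probiotic or Placebo Capsules in V.b.

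2. **Does either label name the allocation?** No. The V.b capsule label names both products, and the V.a label names neither. A woman who sees only her own bottles learns nothing from them. She has already agreed, under the inclusion criteria, to "ingest Lp299v + standard PNVI or standard PNVI + placebo daily through delivery". The labels are informative only to someone who knows both wordings and which arm each belongs to.

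3. **Does another section set a common label?** No. The V.b sentence on taste and packing may cover containers or only the capsule product, and it does not mention label wording. Part IV (Randomization) says nothing on blinding. In the text available, blinding appears only in titles in the reference list. The COVID-19 refill paragraph describes one procedure without distinguishing the arms, which suggests common handling, but it does not say what the labels read.

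4. **Who handles the containers?** Study staff, at pill counts. Part VI schedules pick-ups at about 18-19, 22-23, 30-31 and 38-39 weeks, plus research visits at 24-28 and 34-36 weeks: 4 + 2 = 6 in-person occasions after randomization. The inclusion criteria ask women to "come to UIC on 4-5 occasions" for pick-ups, so the upper count is 5 + 2 = 7. Late starters and early deliveries have fewer. Staff may also deliver supplements to the home. These are opportunities to see a label and do not measure bias. Under the COVID-19 changes a pill count by video call could still show a label; one by voice call could not.

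5. **What is collected on those occasions?** The GI checklist at pick-ups and research visits, adverse events reported at study and adherence visits (part XIV), and interviewer-administered surveys at the two research visits. Of the 17 instruments listed for those visits, 8 fall in domains named by Exploratory Aim 1, by their descriptions in the plan: 3 depression, 2 stress, 2 anxiety and 1 social support (3 + 2 + 2 + 1 = 8). The baseline surveys are not exposed, because randomization follows the baseline visit.

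6. **Do the same people count pills and collect outcomes?** Not stated. Part VI refers to 'we', research staff and trained staff. It neither assigns the tasks to one person nor separates them.

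7. **Is the supply difference a further cue?** Hardly. Thirty days lies within 30-40, and part VI gives a 30-40-day allotment at later visits without distinguishing the arms.

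**The case against.** The strongest reply is that this is a drafting slip. A label that reads Probiotic or Placebo makes sense only as a blinded label for both arms, and a generic label likewise serves to hide the content. The two sentences look like two drafts of one neutral label, each left in a different arm description. That is the more likely explanation, and the documents do not show that differing labels were intended or dispensed. It does not remove the point: the protocol is what the pharmacy and staff work from, and read literally it gives the worse result.

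The second reply concerns tolerability. A reader might infer that the Aim 4 tolerability comparison is itself compromised. The documents do not support that. Parts VI and VI.c name phone, email and text as the route, and no section says that the visit checklist feeds the tolerability criterion. The statistical analysis section compares adverse event counts between groups without naming their source, so a contribution from visit reports is possible but not stated.

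The third reply concerns time and outcome. From 17 March 2020 surveys are by phone or link and refills are mailed, which limits exposure after that date. Aims 1 to 3 rest on laboratory measurements. Both limits stand.

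**Conclusion.** The label sentences in V.a and V.b conflict with the purpose of a matched placebo and need to be reconciled. The risk is conditional on three things: that labels were printed as written, that staff knew both wordings, and that the staff who handled containers also collected outcomes. The documents establish none of the three and exclude none.

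If all three hold, the exposed data are the visit-collected GI checklist and adverse event reports, and the Exploratory Aim 1 surveys given by interview. A reader might go further and infer that the trial was unblinded, that women learned their arm, or that the iron results are biased. The text supports none of these. Nor would the fraction of contacts held in person gauge the damage: a staff member who has once linked a label to an arm takes that knowledge into later calls, and one who has not is unaffected at any visit. The presence and size of any bias cannot be derived.

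The severity is minor to should-fix. The outcomes concerned are secondary or exploratory in kind, but the correction costs almost nothing.

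**What to change.** Replace the two label sentences in V.a and V.b with one sentence requiring identical containers and identical neutral label wording in both arms, and apply it to the mailed refills in the COVID-19 section. State that staff who collect symptoms and administer surveys are blinded to arm. As a minor reconciliation, use one baseline supply statement for both arms.

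For women already enrolled, check which labels were dispensed. If they differed by arm, report this with the symptom and survey results.

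The cost is a wording change, one pharmacy label template and a check of labels already dispensed. It cannot undo exposure that has already occurred.
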